12.1.2. Disease Parameters

Measurable disease. Measurable lesions are defined as those that can be accurately measured in at least one dimension (longest diameter to be recorded) as $\geq 20 \text{ mm}$ ($\geq 2 \text{ cm}$) by chest x-ray or as $\geq 10 \text{ mm}$ ($\geq 1 \text{ cm}$) with CT scan, MRI, or calipers by clinical exam. All tumor measurements must be recorded in millimeters (or decimal fractions of centimeters).

Note: Tumor lesions that are situated in a previously irradiated area might or might not be considered measurable. *If the investigator thinks it appropriate to include them, the conditions under which such lesions should be considered must be defined in the protocol.*

Malignant lymph nodes. To be considered pathologically enlarged and measurable, a lymph node must be $\geq 15 \text{ mm}$ ($\geq 1.5 \text{ cm}$) in short axis when assessed by CT scan (CT scan slice thickness recommended to be no greater than 5 mm [0.5 cm]). At baseline and in follow-up, only the short axis will be measured and followed.

Non-measurable disease. All other lesions (or sites of disease), including small lesions (longest diameter <10 mm [<1 cm] or pathological lymph nodes with \geq 10 to <15 mm [\geq 1 to <1.5 cm] short axis), are considered non-measurable disease. Bone lesions, leptomeningeal disease, ascites, pleural/pericardial effusions, lymphangitis

cutis/pulmonitis, inflammatory breast disease, and abdominal masses (not followed by CT or MRI), are considered as non-measurable.

Note: Cystic lesions that meet the criteria for radiographically defined simple cysts should not be considered as malignant lesions (neither measurable nor non-measurable) since they are, by definition, simple cysts.

'Cystic lesions' thought to represent cystic metastases can be considered as measurable lesions, if they meet the definition of measurability described above. However, if noncystic lesions are present in the same patient, these are preferred for selection as target lesions.

Target lesions. All measurable lesions up to a maximum of 2 lesions per organ and 5 lesions in total, representative of all involved organs, should be identified as **target lesions** and recorded and measured at baseline. Target lesions should be selected on the basis of their size (lesions with the longest diameter), be representative of all involved organs, but in addition should be those that lend themselves to reproducible repeated measurements. It may be the case that, on occasion, the largest lesion does not lend itself to reproducible measurement in which circumstance the next largest lesion which can be measured reproducibly should be selected. A sum of the diameters (longest for non-nodal lesions, short axis for nodal lesions) for all target lesions will be calculated and reported as the baseline sum diameters. If lymph nodes are to be included in the sum, then only the short axis is added into the sum. The baseline sum diameters will be used as reference to further characterize any objective tumor regression in the measurable dimension of the disease.

Non-target lesions. All other lesions (or sites of disease) including any measurable lesions over and above the 5 target lesions should be identified as **non-target lesions** and should also be recorded at baseline. Measurements of these lesions are not required, but the presence, absence, or in rare cases unequivocal progression of each should be noted throughout follow-up.

12.1.3. Methods for Evaluation of Measurable Disease

All measurements should be taken and recorded in metric notation using a ruler or

calipers. All baseline evaluations should be performed as closely as possible to the beginning of treatment and never more than 4 weeks before the beginning of the treatment.

The same method of assessment and the same technique should be used to characterize each identified and reported lesion at baseline and during follow-up. Imaging-based evaluation is preferred to evaluation by clinical examination unless the lesion(s) being followed cannot be imaged but are assessable by clinical exam.

Clinical lesions: Clinical lesions will only be considered measurable when they are superficial (*e.g.*, skin nodules and palpable lymph nodes) and $\geq 10 \text{ mm}$ ($\geq 1 \text{ cm}$) diameter as assessed using calipers (*e.g.*, skin nodules). In the case of skin lesions, documentation by color photography, including a ruler to estimate the size of the lesion, is recommended.

Chest x-ray: Lesions on chest x-ray are acceptable as measurable lesions when they are clearly defined and surrounded by aerated lung. However, CT is preferable.

Conventional CT and MRI: This guideline has defined measurability of lesions on CT scan based on the assumption that CT slice thickness is 5 mm (0.5 cm) or less. If CT scans have slice thickness greater than 5 mm (0.5 cm), the minimum size for a measurable lesion should be twice the slice thickness. MRI is also acceptable in certain situations (*e.g.* for body scans).

Use of MRI remains a complex issue. MRI has excellent contrast, spatial, and temporal resolution; however, there are many image acquisition variables involved in MRI, which greatly impact image quality, lesion conspicuity, and measurement. Furthermore, the availability of MRI is variable globally. As with CT, if an MRI is performed, the technical specifications of the scanning sequences used should be optimized for the evaluation of the type and site of disease. Furthermore, as with CT, the modality used at follow-up should be the same as was used at baseline and the lesions should be measured/assessed on the same pulse sequence. It is beyond the scope of the RECIST guidelines to prescribe specific MRI pulse sequence parameters for all scanners, body parts, and diseases. Ideally, the same type of scanner should be used and the image acquisition protocol should be followed as closely as possible to prior scans. Body scans should be performed with breath-hold scanning techniques, if possible.

PET-CT: At present, the low dose or attenuation correction CT portion of a combined PET-CT is not always of optimal diagnostic CT quality for use with RECIST measurements. However, if the site can document that the CT performed as part of a PET-CT is of identical diagnostic quality to a diagnostic CT (with IV and oral contrast), then the CT portion of the PET-CT can be used for RECIST measurements and can be used interchangeably with conventional CT in accurately measuring cancer lesions over time. Note, however, that the PET portion of the CT introduces additional data which may bias an investigator if it is not routinely or serially performed.

Ultrasound: Ultrasound is not useful in assessment of lesion size and should not be used as a method of measurement. Ultrasound examinations cannot be reproduced in their entirety for independent review at a later date and, because they are operator dependent, it cannot be guaranteed that the same technique and measurements will be taken from one assessment to the next. If new lesions are identified by ultrasound in the course of the study, confirmation by CT or MRI is advised. If there is concern about radiation exposure at CT, MRI may be used instead of CT in selected instances.

Endoscopy, Laparoscopy: The utilization of these techniques for objective tumor evaluation is not advised. However, such techniques may be useful to confirm complete pathological response when biopsies are obtained or to determine relapse in trials where recurrence following complete response (CR) or surgical resection is an endpoint.

Tumor markers: If markers are initially above the upper normal limit, they must normalize for a patient to be considered in complete clinical response. Specific guidelines for both CA-125 response in recurrent ovarian cancer have been published [*JNCI* 96:487-488, 2004; *J Clin Oncol* 17, 3461-3467, 1999; *J Clin Oncol* 26:1148-1159, 2008]. In addition, the Gynecologic Cancer Intergroup has developed CA-125 progression criteria

which are to be integrated with objective tumor assessment for use in first-line trials in ovarian cancer [*JNCI* 92:1534-1535, 2000].

Cytology, Histology: These techniques can be used to differentiate between partial responses (PR) and complete responses (CR) in rare cases (*e.g.*, residual lesions in tumor types, such as germ cell tumors, where known residual benign tumors can remain).

The cytological confirmation of the neoplastic origin of any effusion that appears or worsens during treatment when the measurable tumor has met criteria for response or stable disease is mandatory to differentiate between response or stable disease (an effusion may be a side effect of the treatment) and progressive disease.

FDG-PET: While FDG-PET response assessments need additional study, it is sometimes reasonable to incorporate the use of FDG-PET scanning to complement CT scanning in assessment of progression (particularly possible 'new' disease). New lesions on the basis of FDG-PET imaging can be identified according to the following algorithm:

- a. Negative FDG-PET at baseline, with a positive FDG-PET at follow-up is a sign of PD based on a new lesion.
- b. No FDG-PET at baseline and a positive FDG-PET at follow-up: If the positive FDG-PET at follow-up corresponds to a new site of disease confirmed by CT, this is PD. If the positive FDG-PET at follow-up is not confirmed as a new site of disease on CT, additional follow-up CT scans are needed to determine if there is truly progression occurring at that site (if so, the date of PD will be the date of the initial abnormal FDG-PET scan). If the positive FDG-PET at follow-up corresponds to a pre-existing site of disease on CT that is not progressing on the basis of the anatomic images, this is not PD.
- c. FDG-PET may be used to upgrade a response to a CR in a manner similar to a biopsy in cases where a residual radiographic abnormality is thought to represent fibrosis or scarring. The use of FDG-PET in this circumstance should be prospectively described in the protocol and supported by disease-specific medical literature for the indication. However, it must be acknowledged that both approaches may lead to false positive CR due to limitations of FDG-PET and biopsy resolution/sensitivity.

Note: A 'positive' FDG-PET scan lesion means one that is FDG avid with an uptake greater than twice that of the surrounding tissue on the attenuation corrected image.

12.1.4. Response Criteria

12.1.4.1. Evaluation of Target Lesions

Complete Response (CR): Disappearance of all target lesions. Any pathological lymph nodes (whether target or non-target) must have reduction in short axis to <10 mm (<1 cm).

Partial Response (PR): At least a 30% decrease in the sum of the diameters of target lesions, taking as reference the baseline sum diameters.

Progressive Disease (PD): At least a 20% increase in the sum of the diameters of target lesions, taking as reference the smallest sum on study (this includes the

baseline sum if that is the smallest on study). In addition to the relative increase of 20%, the sum must also demonstrate an absolute increase of at least 5 mm (0.5 cm). (Note: the appearance of one or more new lesions is also considered progressions).

Stable Disease (SD): Neither sufficient shrinkage to qualify for PR nor sufficient increase to qualify for PD, taking as reference the smallest sum diameters while on study.

12.1.4.2 Evaluation of Non-Target Lesions

Complete Response (CR): Disappearance of all non-target lesions and normalization of tumor marker level. All lymph nodes must be non-pathological in size (<10 mm [<1 cm] short axis).

Note: If tumor markers are initially above the upper normal limit, they must normalize for a patient to be considered in complete clinical response.

Non-CR/Non-PD: Persistence of one or more non-target lesion(s) and/or maintenance of tumor marker level above the normal limits.

Progressive Disease (PD): Appearance of one or more new lesions and/or *unequivocal progression* of existing non-target lesions. *Unequivocal progression* should not normally trump target lesion status. It must be representative of overall disease status change, not a single lesion increase.

Although a clear progression of "non-target" lesions only is exceptional, the opinion of the treating physician should prevail in such circumstances, and the progression status should be confirmed at a later time by the review panel (or Principal Investigator).

12.1.4.3 Evaluation Based on CA125

Complete Response (CR): Normalization of CA-125 levels. The response must be confirmed and maintained for at least 28 days. No new or progressive disease on imaging.

Partial Response (PR): At least a 50% reduction in CA-125 levels from a pretreatment sample but not reaching normalization. The response must be confirmed and maintained for at least 28 days. No new or progressive disease on imaging.

Progressive Disease (PD):

- Patients with elevated CA-125 pretreatment and normalization of CA-125 must show evidence of CA-125 greater than, or equal to, 2 times the upper limit of the reference range on 2 occasions at least 1 week apart or
- Patients with elevated CA-125 before treatment, which never normalizes, must show evidence of CA-125 greater than, or equal to, 2 times the nadir value on 2 occasions at least 1 week apart or

- Patients with CA-125 in the reference range before treatment must show evidence of CA-125 greater than, or equal to, 2 times the upper limit of the reference range on 2 occasions at least 1 week apart
- Response determined via measurable disease (measurement of target and nontarget lesions) takes precedence over CA-125 criteria

Stable Disease (SD): CA-125 fluctuations not fitting above criteria

12.1.5 Duration of Response

Duration of overall response: The duration of overall response is measured from the time measurement criteria are met for CR or PR (whichever is first recorded) until the first date that recurrent or progressive disease is objectively documented (taking as reference for progressive disease the smallest measurements recorded since the treatment started). The duration of overall CR is measured from the time measurement criteria are first met for CR until the first date that progressive disease is objectively documented.

Duration of stable disease: Stable disease is measured from the start of the treatment until the criteria for progression are met, taking as reference the smallest measurements recorded since the treatment started, including the baseline measurements.

12.1.5.1 Evaluation of Overall Response

Target	Non-Target Lesions	New Lesions*	Overall Response
Lesions			
CR	CR	No	CR
CR	Non-CR/Non-PD	No	PR
CR	Not evaluated	No	PR
PR	Non-CR/Non-PD/not	No	PR
	evaluated		
SD	Non-CR/Non-PD/not	No	SD
	evaluated		
PD	Any	Yes or No	PD
Any	PD**	Yes or No	PD
Any	Any	Yes	PD

For Patients with Measurable Disease (*i.e.*, Target Disease)

*See RECIST 1.1 manuscript for further details on what is evidence of a new lesion.

**In exceptional circumstances, unequivocal progression in non-target lesions may be accepted as disease progression.

Note: Patients with a global deterioration of health status requiring discontinuation of treatment without objective evidence of disease progression at that time should be reported as "*symptomatic deterioration*." Every effort should be made to document the objective progression even after discontinuation of treatment.

For Patients with Non-Measurable Disease (*i.e.*, Non-Target Disease)

Non-Target Lesions New Lesions Overan Response	Non-Target Lesions	New Lesions	Overall Response
--	--------------------	-------------	------------------

CR	No	CR			
Non-CR/non-PD	No	Non-CR/non-PD*			
Not all evaluated	No	not evaluated			
Unequivocal PD	Yes or No	PD			
Any	Yes	PD			
* 'Non-CR/non-PD' is preferred over 'stable disease' for non-target disease since SD is increasingly used as an endpoint for assessment of efficacy in some trials so to assign this					
category when no lesions can be measured is not advised					

13. DATA REPORTING / REGULATORY REQUIREMENTS

Adverse event lists, guidelines, and instructions for AE reporting can be found in Section 7.0 (Adverse Events: List and Reporting Requirements).

13.1. Study Oversight

This protocol is monitored at several levels, as described in this section. The Protocol Principal Investigator is responsible for monitoring the overall conduct and progress of the clinical trial, including the ongoing review of accrual, patient-specific clinical and laboratory data, and routine and serious adverse events; reporting of expedited adverse events; and accumulation of reported adverse events from other trials testing the same drug(s).

All studies are also reviewed in accordance with the UPMC Hillman Cancer Center data safety monitoring plan (DSMP).

13.2. Data Reporting

13.2.1. Responsibility for Data Submission

Investigator/Sub-investigators, regulatory, CRS management, clinical research coordinators, clinical research associates, data managers, and clinic staff meet monthly in the UPMC Hillman Cancer Center Data Safety Monitoring Board (DSMB) to review and discuss study data to include, but not limited to, the following:

- serious adverse events
- subject safety issues
- recruitment issues
- accrual
- protocol deviations
- breaches of confidentiality

All toxicities encountered during the study will be evaluated on an ongoing basis according to the NCI Common Toxicity Criteria version 5.0 or Patient Reported Outcomes-Common Terminology Criteria for Adverse Events (PRO-CTCAE). All study treatment associated adverse events that are both serious and unexpected will be reported to the IRB. Any modifications necessary to ensure subject safety and decisions to continue, or close, the trial to accrual are also discussed during these meetings. If any literature becomes available which changes the risk/benefit ratio or suggests that conducting the trial is no longer ethical, the IRB will be notified in the form of an Unanticipated Problem submission and the study may be terminated.
All study data reviewed and discussed during these meetings will be kept confidential. Any breach in subject confidentiality will be reported to the IRB in the form of an Unanticipated Problem submission. The summaries of these meetings are forwarded to the UPMC Hillman Cancer Center DSMC, which also meets monthly following a designated format.

For all research protocols, there will be a commitment to comply with the IRB's policies for reporting unanticipated problems involving risk to subjects or others (including adverse events). DSMC progress reports, to include a summary of all serious adverse events and modifications, and approval will be submitted to the IRB at the time of renewal.

Both the UPMC Hillman Cancer Center DSMC as well as the individual disease center DSMB have the authority to suspend accrual or further investigate treatment on any trial based on information discussed at these meetings.

14. STATISTICAL CONSIDERATIONS

14.1 Study Design/Endpoints

Primary endpoint is defined as the time to next therapy from completion of platinum-based therapy for treatment of recurrence until initiation of post-olaparib treatment. Based on Ledermann et al,²⁹ the expected median time to progression on olaparib following platinum response is 8.4 months for a cohort with 22% *BRCA* mutation prevalence.

Secondary endpoints

Progression-free survival is defined as the time from enrollment until detected recurrence or progression of disease, via RECISTv1.1, or death from any cause.

- Overall survival as defined as the time from enrollment to death from any cause.
- Toxicity rates defined by the National Cancer Institute's Common Terminology Criteria for Adverse Events (CTCAE) v5.0.
- Response rate as defined by RECIST or CA-125 and stratified by *BRCA* mutation status.
- Patient-reported adverse events using the NCI Patient Reported Outcomes-Common Terminology Criteria for Adverse Events (PRO-CTCAE) (See Appendix
- Health-related quality of life measured via The Functional Assessment of Cancer Therapy + Ovarian-specific scale (FACT-O)
- Physical function assessed through the PROMIS Physical Function-20a assesses self-reported performance of physical activities
- Worry and distress measured via Assessment of Survivor Concerns (ASC) Worry Subscale and Impact of Event Scale (IES-R)
- Financial toxicity measured through

a) monetary measure using the Modified Collection of Indirect and Nonmedical Direct Costs (COIN),

b) objective measure of financial burden assessed using Barrera et al.'s Economic Hardship questionnaire⁵¹, and

c) subjective measure of financial distress will be gauged using the Comprehensive Score for Financial Toxicity (COST Measure).

• Exposure measured through quantitating olaparib by LC-MS/MS in a trough sample.

PLANNED ENROLLMENT REPORT

Page 37 of

Racial Categories	Ethnic Cate	Total		
	Not Hispanic or Latino	Hispanic or Latino		
	Female	Female		
American Indian/ Alaska Native	0	0	0	

	Ethnic Cat		
Racial Categories	Not Hispanic or Latino	Hispanic or Latino	Total
	Female	Female	
Asian	3	0	3
Native Hawaiian or Other Pacific Islander	0	0	0
Black or African American	7	0	7
White	65	0	65
More Than One Race	0	0	0
Total	75	0	75

13.2 SAMPLE SIZE/ACCRUAL RATE

Study 19 is the only PARP inhibitor maintenance trial in the platinum sensitive recurrent setting to report both PFS and OS data. Median progression-free survival was 8.4 months in the olaparib group versus 4.8 months in the placebo group (hazard ratio for progression or death, 0.35; 95% confidence interval [CI], 0.25 to 0.49; P<0.001). The secondary end point of time to progression according to the RECIST guidelines or CA-125 level, whichever showed earlier progression, was also significantly longer in the olaparib group than in the placebo group (median, 8.3 months vs. 3.7 months; hazard ratio for progression, 0.35; 95% CI, 0.25 to 0.47; P<0.001). There was no statistically significant OS advantage noted for those treated with olaparib; for the entire population median OS was 29.8-months-[95%-CI-26·9–35·7]-in the olaparib arm vs 27.8 months-[24·9–33·7] in the placebo arm. For those patients evaluable for response (n=61), there were 16 (26.2%) either PR or CR by RECIST and 1 (1.6%) by CA125²⁹.

Using the reported data from Study 19, we will assess whether delaying olaparib until biochemical relapse will increase the median time to next treatment by \sim 3 months (from 8 to 11 months). We assume 3-4 patients can be accrued/month and that the *BRCA* mutation

prevalence will be ~20% and thereby be comparable to the historical control group. With 2 years of accrual and 18 months of additional follow up, we will require 75 eligible patients. This will allow 90% power for a level 0.10 one-sided one sample exponential test to detect an improvement in median time to next treatment from 8 to 11 months. Due to the possibility of lost to long-term follow-up, we plan to accrue an additional 10% of the targeted accrual. Therefore, the sample size for this study will be approximately 83 patients in order to successfully accrue 75 evaluable patients.

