with disease, striking a balance between drug toxicity and treatment to alleviate symptom burden from disease. Based on Study 19 data where progression free survival in the placebo arm was 4.8 months and the progression free survival in olaparib treatment arm was 8.4 months, we estimated that by waiting to start olaparib until biochemical relapse will extend time to next treatment by 3 months (8 to 11 months) beyond that reported in the olaparib arm of Study 19.

If this treatment approach is superior or even non-inferior with regard to time to next therapy, it would be an important paradigm shift in the way we use these drugs, leading to similar efficacy outcomes, while decreasing the financial burden and improving overall quality of life. Moreover, by collecting tissue samples before and after treatment and evaluating for resistance mechanisms, PDX models developed from these samples can be used to test for combinations that may reverse the effects of the resistance and/or restore sensitivity to PARP-I, allowing for its use later on in a patient's treatment course.

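### The primary test's null of 8 months lies below both Study 19 olaparib progression medians the protocol cites (8.4 and 8.3), and neither of these is a time to next treatment

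*Combined protocol and SAP*

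**What the plan says.** Section 14.1 defines the primary endpoint as "the time to next therapy from completion of platinum-based therapy for treatment of recurrence until initiation of post-olaparib treatment". It then says that "the expected median time to progression on olaparib following platinum response is 8.4 months for a cohort with 22" percent BRCA mutation prevalence.

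The section headed Sample Size/Accrual Rate (13.2) reports two Study 19 progression results: "Median progression-free survival was 8.4 months in the olaparib group versus 4.8 months in the placebo group", and, for progression by RECIST or CA-125, "median, 8.3 months vs. 3.7 months". Citing those data, it sets a one-sided 0.10 one-sample exponential test with 90% power to detect "an improvement in median time to next treatment from 8 to 11 months". It needs 75 eligible patients, accrued over 2 years with 18 further months of follow-up. On case mix, it expects that BRCA mutation "prevalence will be ~20% and thereby be comparable to the historical control group".

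The Rationale (2.4) quotes the Study 19 PFS medians of 4.8 and 8.4 months and, in the same sentence, says the delayed start "will extend time to next treatment by 3 months (8 to 11 months) beyond that reported in the olaparib arm of Study 19". Section 13.3.4 treats rejection as evidence that time to next treatment is longer than with undelayed olaparib. It also plans a Kaplan-Meier median with a 90% confidence interval.

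**The concern.** In a single-arm trial the historical null is the only comparator, so its value and its endpoint decide what a positive result means. Both are in doubt here.

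- **Value.** The null of 8 is lower than each progression median it could have come from. Case mix does not explain it, because the plan calls its expected prevalence comparable with the historical group. Rounding is plausible but is not stated, and it favours the treatment.
- **Endpoint.** The Rationale presents 8 months as a time to next treatment reported in Study 19, but the figure it gives is PFS. No immediate-start median time to next treatment appears anywhere in the document. The clock may differ too: this endpoint starts at completion of platinum, enrollment may come up to 8 weeks later (3.1.11), and Study 19's time origin is not given.

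The stakes are the main conclusion. The Rationale says: "If this treatment approach is superior or even non-inferior with regard to time to next therapy", it would be an important change in how these drugs are used. A null set too low makes that claim easier to reach. A null on another endpoint leaves the claim unsupported even if the number is corrected.

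**Working it through.** **Inputs** (Sample Size/Accrual Rate section): n = 75; uniform accrual over 24 months plus 18 months of follow-up; one-sided alpha 0.10 (z = 1.2816); exponential times; medians 8 (null) and 11 (alternative). Cited Study 19 olaparib medians: 8.4 and 8.3.

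**Expected events.** With L = ln 2 / m, the probability that an event is observed is p(m) = 1 − [exp(−18L) − exp(−42L)] / (24L).

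| Median m (months) | p(m) | Events, 75 × p |
|---|---|---|
| 8 | 0.9115 | 68.4 |
| 8.3 | 0.9040 | 67.8 |
| 8.4 | 0.9014 | 67.6 |
| 11 | 0.8342 | 62.6 |
| 11.4 | 0.8239 | 61.8 |

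**Rejection probability** for null m0 and true median m1, on the log hazard scale:

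Φ{ [ln(m1/m0) − 1.2816/√d0] × √d1 }, where d0 and d1 are the expected events at m0 and m1.

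**Reproducing the plan.** For 8 versus 11: ln(11/8) = 0.3185 and 1.2816/√68.4 = 0.1550, so (0.3185 − 0.1550) × √62.6 = 1.29 and power is 90.2%. The smallest n giving 90% is 75. The stated design reproduces, so the arithmetic is sound and the question is only the null.

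**Null 8 when the truth is a cited Study 19 value**

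- True 8.4: ln(8.4/8) = 0.0488, and (0.0488 − 0.1550) × √67.6 = −0.87, giving 19.1% (17.5% in a simulation of 100,000 trials).
- True 8.3: ln(8.3/8) = 0.0368, and (0.0368 − 0.1550) × √67.8 = −0.97, giving 16.5% (15.3% simulated).
- True 8, for comparison: 10% by the formula, 8.9% simulated.

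**Estimated exponential median needed to reject**, m0 × exp(1.2816/√d0)

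- Null 8: 8 × exp(0.1550) = 9.34 months.
- Null 8.4: 8.4 × exp(0.1559) = 9.82 months.

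**Power with null 8.4 and n = 75**

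- True 11.4 (3-month gain kept): (0.3054 − 0.1559) × √61.8 = 1.18, giving 88.0% (87.0% simulated). Reaching 90% would take 82 evaluable patients.
- True 11: (0.2697 − 0.1559) × √62.6 = 0.90, giving 81.6% (80.3% simulated). Reaching 90% would take 105.

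**Endpoint mismatch.** This cannot be computed from the document. Next therapy usually starts at or after progression, which would make a progression median too low as a benchmark. But a patient who stops for toxicity may start another therapy before progressing, and Study 19's time origin is unknown, so the net direction is not fixed. As an assumption only: if the immediate-start median time to next treatment were 9, 9.5 or 10 months, the test against 8 would reject about 38%, 55% or 71% of the time.

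**The case against.** The strongest reply is that 8 is openly rounded from 8.4. The figures stand side by side, the gap is 0.3 to 0.4 months against a 3-month target, and few trials would turn on it. With a true median of 8.4 the rejection rate differs by 19.1 − 10 = about 9 points between the two nulls; with a true 11 it differs by 90.2 − 81.6 = about 9 points. The test also holds its level at its stated null. The 18-19% counts as error only if 8.4 is the right reference, and the second half of the concern says it is a different endpoint. Finally, this is a phase IIA trial whose synopsis objective is to estimate, and the planned Kaplan-Meier interval does not depend on the null.

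Much of this is fair. The inflated rate is conditional on the plan's own expected median, and the rounding effect is moderate. The endpoint mismatch is the weightier part, and it has no computable size. The Rationale does disclose that its source figure is PFS.

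The concern survives nonetheless. Section 13.3.4 specifies a formal test and a comparative reading of it, no reason for 8 is given, and the Rationale calls the benchmark a reported time to next treatment. If the proxy is accepted, the plan's own value for it is 8.4. If it is not accepted, the comparative claim has no benchmark at all.

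**Conclusion.** The concern holds on both parts. Judged against the plan's own 8.4-month benchmark, the test declares an improvement about 18-19% of the time when there is none, against a stated 10%; for 8.3 months the figure is about 15-17%. These rates assume exponential times, uniform accrual, 75 evaluable patients and no loss to follow-up. Separately, correcting the number would not make rejection evidence of a longer time to next treatment than with immediate olaparib, because the benchmark measures progression. No rate is claimed for that second part. Since the null fixes the primary conclusion and cannot credibly be changed once results are known, it must be corrected before the primary analysis.

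**What to change.** 1. In the Sample Size/Accrual Rate section, set the null at 8.4 months. Keep 75 evaluable patients and the 3-month gain, and restate the design as 8.4 to 11.4 months with about 87-88% power. Note that power is about 80-82% if the alternative stays at 11.
2. There and in the Rationale (2.4), state that 8.4 is a proxy derived from PFS, not a reported time to next treatment.
3. In 13.3.4, describe rejection as exceeding that proxy. Claim an improvement over immediate-start olaparib only if an immediate-start median time to next treatment, counted from completion of platinum, serves as the benchmark. That figure would have to come from outside this document.
4. Otherwise rest the conclusion on the planned Kaplan-Meier median with its 90% interval, which matches the estimation objective. If the interval's lower limit is compared with a benchmark, say that this corresponds to one-sided 0.05, stricter than the planned 0.10.

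The cost is wording in three sections and no added patients. Stated power falls from 90% to about 87-88%, and the conclusion is narrower. Restoring 90% power is optional: it would take about 82 evaluable patients for 11.4 months, or 105 for 11.
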